6. GENERAL ANALYSIS DEFINITIONS

6.1 TREATMENTS

For safety analyses, data up to and including 28 days after last treatment intake will be considered as on-treatment.

Patients will be analysed according to the treatment group initially assigned. All planned analysis will be presented by this treatment group. Handling of patients where treatment group assignment has not been followed will be handled on a case-by-case basis, to be agreed at report planning meetings.

Analyses for Regimen M and Regimen U will be presented separately.

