## CLINICAL TRIAL PROTOCOL SYNOPSIS

Name of company: Boehringer Ingelheim		Tabulated Trial Protocol
Name of finished product: Not Applicable		
Name of active ingredient: BIBW 2992		
Protocol date 3 April 2009	Trial number 1200.38	Planned trial period July 2009 – Jun 2015
Title of trial: Phase I, open label trial to explore safety of combining BIBW 2992 and Radiotherapy with or without Temozolomide in newly diagnosed GBM		
Co-ordinating Investigator: [REDACTED] Tel: [REDACTED] /Fax: [REDACTED]		
Trial sites: Multicenter Trial		
Clinical phase: I		
Objectives: Regimen U: Determination of the maximum tolerated dose (MTD) of BIBW 2992 administered in combination with radiotherapy in patients with newly diagnosed malignant gliomas (WHO grade IV) with an unmethylated MGMT-promoter. Regimen M: Determination of the maximum tolerated dose (MTD) of BIBW 2992 in combination with TMZ and radiotherapy in patients with newly diagnosed malignant gliomas (WHO grade IV) with a methylated or an unmethylated MGMT-promoter.		
Methodology: Open-label, stratified (Phase I) study		
No. of patients: total: Up to 60 patients each treatment: Up to 30 patients in each regimen (2-regimen study);		
Diagnosis and main criteria for inclusion: - Newly diagnosed malignant glioma (WHO Grade IV). - Tumour material available for MGMT testing unless MGMT test results already available.		
Test products: BIBW 2992 (film-coated tablets)		
dose: During RT (6 weeks): Regimen U and M: Dose escalation of daily BIBW2992 (20,40 mg) with one de-escalation step (30 mg) in case 40mg is not tolerated. After RT: Regimen U: 40 mg/day BIBW 2992 until either progressive disease or undue adverse reaction, whichever occurs first. Regimen M: 40 mg/day during concomitant TMZ/ BIBW 2992 treatment period followed by 40 mg/day BIBW 2992 monotherapy until either progressive disease or undue adverse reaction, whichever occurs first.		

Name of company: Boehringer Ingelheim		Tabulated Trial Protocol	
Name of finished product: Not Applicable			
Name of active ingredient: BIBW 2992			
Protocol date 3 April 2009	Trial number 1200.38	Planned trial period July 2009 – Jun 2015	
mode of admin. : Oral			

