#### 4.1.3 Selection of doses in the trial

For the concomitant radiochemotherapy phase, the chosen starting dose of BIBW 2992 in this study is 20 mg, which has been a tolerable dose when combining BIBW 2992 with different types of chemotherapy (U03-3218). In the current trial, BIBW 2992 dose escalation will stop at a maximum dose of 40 mg daily (section 4.1.4.1.1), which is an effective dose for BIBW 2992 monotherapy for continuous dosing (U03-3218).

For the maintenance phase, 40 mg daily in both treatment regimens will be administered. Data from trial 1200.36 indicate that 40mg of BIBW 2992 in combination with TMZ is well tolerated.

The dose schedule in Regimen U and M are described in figure 4.1.3: 1 and 4.1.3: 2 respectively

[figure not shown]

Figure 4.1.3: 1 Dosing schedule Regimen U (Unmethylated MGMT)

[figure not shown]

Figure 4.1.3: 2 Dosing schedule Regimen M (Methylated MGMT or Unmethylated MGMT after determination of regimen U MTD)

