A3.6	Requirement for treatment with P-gp inhibitors or P-gp inducers	For patients enrolled after implementation of CTP amendment 2 only: Exclusion criteria EX23 is met.
B	Informed consent	
B1	Informed consent not given	
B1.1	Informed consent 1 not given	For patients enrolled before implementation of CTP amendment 3 and who do not already have an MGMT test result only: Inclusion criteria IN7 is not met. or Date of informed consent 1 is missing.
B1.2	Informed consent 2/3 not given	Inclusion criteria IN7 is not met. or Date of informed consent 2/3 is missing.
B2	Informed consent given too late	
B2.1	Informed consent 1 given too late	For patients enrolled before implementation of CTP amendment 3 and who do not already have an MGMT test result only: Date of any study specific procedures before date of informed consent 1.
B2.2	Informed consent 2/3 given too late	Date of any study specific procedures before date of informed consent 2/3.
C	Trial medication and randomisation	
C1	Incorrect trial medication taken	
C1.1	Incorrect TMZ dosing during concomitant treatment period (Regimen M only)	For patients in Regimen M only: At least one TMZ dose during concomitant treatment period not according to the dose described in Section 4.1.4.2 of the CTP.
C2	Treatment group assignment not followed	
C2.1	Afatinib treatment during concomitant treatment period in discordance with treatment group assignment	Initial dose of afatinib does not correspond to treatment group assignment. or Afatinib dose changes during concomitant treatment period not according to the dose reduction scheme described in Section 4.1.4.1.2 of the CTP.
C2.2	TMZ treatment during concomitant treatment period in discordance with treatment group assignment	For patients in Regimen M only: No dose of TMZ during concomitant period. or For patients in Regimen U only: At least one dose of TMZ during concomitant treatment period.
C3	Non-compliance	
C3.1	Afatinib non-compliance during concomitant treatment period	Total number of doses of afatinib missed for reasons other than AE is more than 8 during concomitant treatment period. or Number of consecutive doses of afatinib missed for non-AE reasons is more than 5 during concomitant treatment period.

[figure not shown]
Table 6.2: 1 Important Protocol Violations (continued)

Category / Code	Description	Comment/Example

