7.8 SAFETY ANALYSIS

7.8.1 Adverse events

The analyses of AEs will be descriptive in nature. All analyses of AEs will be based on the number of patients with AEs (not the number of AEs). For this purpose, AE data will be combined in a 2-step procedure into AE records.

In a first step, AE occurrences, i.e. AE entries on the case report form, will be collapsed into AE episodes provided that all of the following applies:

- The same Medical Dictionary for Regulatory Activities (MedDRA) lowest level term was reported for the occurrences,
- The occurrences were time-overlapping or time-adjacent (time-adjacency of 2 occurrences is given if the second occurrence started on the same day or on the day after the end of the first occurrence),
- Treatment did not change between the onset of the occurrences or treatment changed between the onset of the occurrences, but no deterioration was observed for the later occurrence.

In a second step, AE episodes will be condensed into AE records provided that the episodes were reported with the same term on the respective MedDRA level and that the episodes are

assigned to the same treatment. For further details on summarisation of AE data, please refer to BI standards for AEs. (5)

CTCAE grade and investigator-defined DLT will be included as additional AE attributes. For the purposes of collapsing, additional deterioration rules will be defined for both attributes. In addition, in this trial, the standard AE attribute 'action taken with trial drug' is separated for afatinib and TMZ; the standard condensing rules will be applied for both.

The analysis of AEs will be based on the concept of treatment emergent adverse events. That means that all AEs occurring between first administration of trial medication until 28 days after last administration of trial medication will be assigned to trial medication. All AEs occurring before first administration of trial medication will be assigned to 'screening' and all AEs occurring after last administration of trial medication + 28 days will be assigned to 'post-study'.

Any AE meeting the criteria for DLT (defined in Section 5.2.2 of the CTP), regardless of date of onset, will be considered an SAE or SIAE.

According to ICH E3 (6), AEs classified as 'other significant' will include those non-serious and non-significant AEs:

- (i) with 'action taken = discontinuation' or 'action taken = reduced', or

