- (ii) with marked haematological and other lab abnormalities or which lead to significant concomitant therapy as identified by the Trial Clinical Monitor/Investigator at a report planning meeting.

An overall summary of AEs will be presented, this will include the additional AE attributes maximum CTCAE grade and investigator defined DLT.

The frequency of patients with AEs will be summarised by treatment, primary system organ class (SOC) and preferred term (PT). Separate tables will be provided for patients with other significant AEs according to ICH E3 (5), for patients with non-serious SIAEs, for patients with SAEs, for patients with investigator defined DLTs and for patients with related AEs. An additional table will be produced of AEs stratified by the attribute maximum CTCAE grade.

The SOCs will be sorted according to the standard sort order specified by European Medicines Agency (EMA), PTs will be sorted by frequency (within SOC).

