7.8.1.1 Adverse events of special interest

The following AEs are considered of special interest for this trial:

- Diarrhoea,
To be identified by the PT 'Diarrhoea';
- Nausea and vomiting,
To be identified by the PTs 'Nausea' and 'Vomiting';
- Rash and acne,
To be defined by the PTs contained within the project-defined special grouped-term category 'RASH/ACNE';

- Other AEs that occur with sufficient overall frequency,
To be determined by the trial team at the report planning meeting prior to database lock.

An overall summary of each of these AEs of special interest will be presented. This will include the additional AE attributes ‘Patients with investigator-defined DLTs’, ‘Maximum CTCAE grade’ and ‘Time to first occurrence’ (see [Section 9.2](#) of this document).

In addition, the frequency of patients with AEs will be summarised by treatment and project-defined special grouped-term category or preferred term. Where applicable, AE PTs will be re-categorised into one of the following grouped-term categories:

- Fatigue (FATIGUE);
- Nail effect (NAILS);
- Ocular effect (OCULAR);
- Rash and acne (RASH/ACNE);
- Stomatitis (STOMA).

Otherwise, AEs will be categorised according to MedDRA PT. Further tables will be provided for patients with related AEs for AEs stratified by the attribute maximum CTCAE grade.

The PTs identified within each of the project-defined special grouped-term categories will be listed.

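### General AE tables by initially assigned dose cohort pool the RT period with maintenance planned at 40 mg, so the lower-dose columns can mix doses; no split by period is visible

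*SAP*

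**What the plan says.** **Columns.** SAP 6.1: "Patients will be analysed according to the treatment group initially assigned. All planned analysis will be presented by this treatment group". The important-violation list (SAP Table 6.2: 1, code C2.1) shows that the group means the starting dose, since one trigger is "Initial dose of afatinib does not correspond to treatment group assignment". Protocol 7.3.3 likewise tabulates AEs by dosage cohort.

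**Window.** SAP 7.8.1: "all AEs occurring between first administration of trial medication until 28 days after last administration of trial medication will be assigned to trial medication". The frequency tables there are laid out by treatment, system organ class and preferred term, with further tables for related AEs and maximum CTCAE grade. For special-interest AEs (SAP 7.8.1.1), "An overall summary of each of these AEs of special interest will be presented", including time to first occurrence. None of these visible layouts has a period dimension.

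**Dose.** The cohort doses apply during the six weeks of RT. Protocol 4.1.3 then states: "For the maintenance phase, 40 mg daily in both treatment regimens will be administered". The synopsis, 4.1.1 and 4.1.4.1 agree. Protocol 4.1.4.1.2 leaves the maintenance dose to case-by-case decision after a reduction during RT. Protocol 4.1.4.1.1, however, rules out escalation within a patient, and 4.1.4.1 bars escalation other than as described there.

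**Timing that is already covered.** SAP 5.1 restricts the primary DLT endpoint to onset in the 42-day concomitant period, and SAP 7.4 lists later DLTs separately. Protocol 7.3.1 records the study period at onset for all AEs that meet the DLT criteria, whether or not judged related.

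**The concern.** The secondary safety endpoint in Protocol 2.3 is the incidence and intensity of AEs as the BIBW 2992 dose increases. A column labelled 20 mg invites the reader to take its entries as the AE profile at 20 mg. If those patients move to 40 mg after RT, part of the column describes 40 mg, and the table alone does not show which part. A reader looking for a dose relation then sees columns that are more alike than the RT-period doses would make them.

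The place where this could be misread is the optional safety analysis in Protocol 7.3.4. It is meant to help select the dose for later studies, and it reports safety observations beyond the concomitant period where feasible. It leaves its details to the SAP, and none are visible there.

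**Working it through.** **Column sizes.** Protocol 7.6 gives 2 regimens × (12 + 6 + 6) = 48 patients, which reproduces its stated figure. One patient is therefore 1/12 = 8.3 points in an expanded cohort, 1/6 = 16.7 points in a cohort of six, and 1/3 = 33.3 points in a cohort of three.

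**Planned share of dosing days at 40 mg.** This is for a 20 or 30 mg patient who stays on treatment and follows the maintenance plan, with 42 days of RT, 28-day cycles, and a further 28-day TMZ break in Regimen M.

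- After 28 maintenance days: 28 / (42 + 28) = 28/70 = 40%.
- Regimen U after cycle 6: 168 / (42 + 168) = 168/210 = 80%.
- Regimen M after cycle 6: (28 + 168) / (42 + 196) = 196/238 = 82%.

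**Effect on a table, as an illustration.** The documents give no AE rates, so every risk here is assumed. Let p be the RT-period risk (5% at 20 mg, 20% at 40 mg, a gap of 15 points). Let m be the risk per six-week maintenance block, the same in both columns because both are taken to be on 40 mg. Let k be the number of blocks. With independent blocks, the pooled column shows 1 − (1 − p)(1 − m)^k.

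| m | 20 mg, k=1 | 40 mg, k=1 | Gap, equal follow-up | 40 mg, k=0 | Gap, 20 mg k=1 and 40 mg k=0 |
|---|---|---|---|---|---|
| 5% | 9.75% | 24.0% | 14.25 | 20% | 10.25 |
| 10% | 14.5% | 28.0% | 13.5 | 20% | 5.5 |
| 20% | 24.0% | 36.0% | 12.0 | 20% | −4.0 |

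With equal follow-up of one block, the shift from 15 points is 0.75, 1.5 or 3 points, which is less than half a patient even in a column of 12. With equal follow-up the gap is 15 × (1 − m)^k, so it shrinks further as maintenance lengthens. At 168 days (k = 4) it is 15 × 0.8145 = 12.2, 15 × 0.6561 = 9.8 or 15 × 0.4096 = 6.1 points. It stays positive throughout.

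**Unequal follow-up.** Protocol 4.1.4.1.1 opens the next cohort only after the previous one has completed 42 days. Take the earliest Protocol 7.3.4 snapshot, with 40 mg as the last cohort and its patients enrolled together. A 20 mg patient still on treatment then has at least 42 maintenance days (42/84 = 50% of dosing days), while the last 40 mg patient has none. The last table column shows this case. The shifts are 4.75, 9.5 and 19 points; the largest is slightly more than one patient in six (16.7).

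**The case against.** **The SAP does what the protocol asks.** Protocol 7.3.3 prescribes tables by dosage cohort, Protocol 7.3 rules out comparisons between cohorts, and a cohort can be read as a planned sequence of RT dose then maintenance. This stands: there is no departure from the protocol and no test is affected. The columns will still be read by dose, because the endpoint is worded that way.

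**Timing is not ignored.** DLTs are split by period. Protocol 7.3.1 gives the period at onset for AEs meeting DLT criteria, related or not, although the visible SAP 7.4 does not repeat that table. Special-interest AEs carry time to first occurrence. This narrows the gap to AEs that do not meet the DLT criteria. Time to first occurrence is not a split by period, and it says nothing of later recurrence or worsening.

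**The mixing may not happen.** If lower-cohort patients do not move to 40 mg, the doses do not mix in this way. The protocol passages conflict, so the point is conditional. A split would still separate time on RT from time after it and, in Regimen M, daily TMZ from five-day cycles.

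**A split may exist out of sight.** Some SAP sections, including 9.2, and the sponsor's AE standard are not available. Only the absence of a visible split can be claimed.

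**A stronger reading to avoid.** A reader might infer from the −4 in the table that dose mixing can reverse the apparent dose order. It does not do so here: the reversal appears only when the 20 mg column has an extra block of follow-up and the 40 mg column has none. That is a separate effect, which the same split also removes.

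**Conclusion.** The concern holds as a reporting weakness in the general AE tables (overall, related, maximum grade, special interest), mainly for AEs that do not meet the DLT criteria. On the plan as written, most of a lower-cohort patient's dosing days can be at 40 mg, yet the visible tables do not separate them. How far this changes the figures is unknown. Under the assumed risks, one equal maintenance block costs 0.75 to 3 of 15 points, longer maintenance costs more, and the largest shift shown (19 points) belongs to unequal follow-up at an early snapshot.

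A reader might go further and infer that the MTD is compromised. The documents do not support that: the primary analysis counts DLTs with onset in the concomitant period only. No hypothesis test is planned, so none is affected.

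The conclusion assumes that lower-cohort patients move to 40 mg as the maintenance passages state, that no unseen section already provides the split, and, for the illustration, independent six-week blocks with the same maintenance risk in both columns. This is a cheap improvement to consider, not an error in the primary analysis.

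**What to change.** 1. Keep the planned whole-treatment AE tables. Footnote them to say that columns are RT-phase dose cohorts and include AEs arising during maintenance.
2. In SAP 7.8.1 and 7.8.1.1, add the overall, related, maximum-grade and special-interest tables split by period of onset or worsening:
   - the concomitant RT period, by cohort within regimen, using the same window as the primary DLT analysis;
   - from the end of that period to 28 days after last dose, by cohort within regimen, with a listing of the dose taken at onset (or, if stopped, the last dose).
3. Before fixing that window, reconcile the 42-day period in SAP 5.1 with Protocol 4.1.4.1.1, which assesses DLTs until RT is finished when the schedule overruns.
4. Treat the two periods as different treatments in the existing collapsing rule. It already merges occurrences where "treatment changed between the onset of the occurrences, but no deterioration was observed for the later occurrence", so an AE that worsens after the change stays separate. One that merely continues remains in the RT period, and the SAP should say so.
5. Carry the period-at-onset attribute of Protocol 7.3.1 into SAP 7.4.
6. Reconcile the protocol passages on within-patient escalation (4.1.4.1, 4.1.4.1.1) with those on maintenance dosing (synopsis, 4.1.1, 4.1.3, 4.1.4.1). No dose is proposed here.

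If an unseen section already gives the split, a cross-reference is enough. The cost is SAP wording and additional tables, many with small cells. Dosing and AE onset dates are already collected, so no new data are needed.

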6.2 IMPORTANT PROTOCOL VIOLATIONS

Important protocol violations (IPVs) are defined according to BI standards (3) and are specified in [Table 6.2: 1](#) of this document. A per protocol set will not be defined for the analysis of this trial but IPVs will be described for patients in the treated set (as defined in [Section 6.3](#) of this document).

Table 6.2: 1 Important Protocol Violations

Category / Code		Description	Comment/Example
A		Entrance criteria not met	
	A1	Diagnosis of trial disease questionable	Inclusion criteria IN1 not met. or Trial diagnosis is not histologically-confirmed WHO Grade IV newly diagnosed malignant glioma.
	A2	MGMT testing	
	A2.1	Methylated MGMT status not proven (Regimen M only)	For patients in Regimen M enrolled before implementation of CTP amendment 3 only: Inclusion criteria IN2 not met. or MGMT test result is not methylated. or Date of MGMT test is missing.
	A2.2	Unmethylated MGMT status not proven (Regimen U only)	For patients in Regimen U enrolled before implementation of CTP amendment 3 only: Inclusion criteria IN2 not met. or MGMT test result is not un-methylated. or Date of MGMT test is missing.
	A2.3	Tumour material not available for MGMT testing or MGMT test results not available	For patients in Regimen M enrolled after implementation of CTP amendment 3 only: Inclusion criteria IN2 not met. or Both of the following: MGMT test result not already available. and Date of MGMT test is missing.
	A3	Safety exclusion criteria met	
	A3.1	Prohibited baseline condition or diagnosis	At least one of exclusion criteria EX6-E11 is met. or At least one baseline condition meeting exclusion criteria (defined in Section 3.3.2 of the CTP).
	A3.2	LVEF assessment indicating inadequate cardiac function	Exclusion criteria EX12 is met. or Screening left ventricular ejection fraction (LVEF) both missing or < 50%.
	A3.3	Laboratory result indicating inadequate organ function	At least one of exclusion criteria EX13-E17 is met. or Screening and baseline laboratory results both missing or meeting exclusion criteria (defined in Section 3.3.2 of the CTP).
	A3.4	Negative pregnancy test result not obtained	Exclusion criteria EX19 is met. or For female patient with reproductive potential, screening pregnancy test is positive or not done.
	A3.5	Hypersensitivity to trial medication	Exclusion criteria EX22 is met.

Table 6.2: 1 Important Protocol Violations (continued)

Category / Code	Description	Comment/Example
A3.6	Requirement for treatment with P-gp inhibitors or P-gp inducers	For patients enrolled after implementation of CTP amendment 2 only: Exclusion criteria EX23 is met.
B	Informed consent	
B1	Informed consent not given	
B1.1	Informed consent 1 not given	For patients enrolled before implementation of CTP amendment 3 and who do not already have an MGMT test result only: Inclusion criteria IN7 is not met. or Date of informed consent 1 is missing.
B1.2	Informed consent 2/3 not given	Inclusion criteria IN7 is not met. or Date of informed consent 2/3 is missing.
B2	Informed consent given too late	
B2.1	Informed consent 1 given too late	For patients enrolled before implementation of CTP amendment 3 and who do not already have an MGMT test result only: Date of any study specific procedures before date of informed consent 1.
B2.2	Informed consent 2/3 given too late	Date of any study specific procedures before date of informed consent 2/3.
C	Trial medication and randomisation	
C1	Incorrect trial medication taken	
C1.1	Incorrect TMZ dosing during concomitant treatment period (Regimen M only)	For patients in Regimen M only: At least one TMZ dose during concomitant treatment period not according to the dose described in Section 4.1.4.2 of the CTP.
C2	Treatment group assignment not followed	
C2.1	Afatinib treatment during concomitant treatment period in discordance with treatment group assignment	Initial dose of afatinib does not correspond to treatment group assignment. or Afatinib dose changes during concomitant treatment period not according to the dose reduction scheme described in Section 4.1.4.1.2 of the CTP.
C2.2	TMZ treatment during concomitant treatment period in discordance with treatment group assignment	For patients in Regimen M only: No dose of TMZ during concomitant period. or For patients in Regimen U only: At least one dose of TMZ during concomitant treatment period.
C3	Non-compliance	
C3.1	Afatinib non-compliance during concomitant treatment period	Total number of doses of afatinib missed for reasons other than AE is more than 8 during concomitant treatment period. or Number of consecutive doses of afatinib missed for non-AE reasons is more than 5 during concomitant treatment period.

[figure not shown]
Table 6.2: 1 Important Protocol Violations (continued)

Category / Code	Description	Comment/Example
C3.2	TMZ non-compliance during concomitant treatment period (Regimen M only)	For patients in Regimen M only: Total number of doses of TMZ missed for reasons other than AE is more than 8 during concomitant treatment period.
C4	Trial specific PVs related to trial medication	
C4.1	Dose reduction scheme for afatinib not followed	Regardless of treatment period, incidence of DLT without subsequent adherence to the dose reduction scheme described in Section 4.1.4.1.2 of the CTP.
C4.2	TMZ treatment continued but re-treatment criteria not met (Regimen M only)	For patients in Regimen M only: Following the concomitant treatment period, TMZ not terminated despite re-treatment criteria described in Section 4.1.4.2 of CTP not met.
D	Concomitant medication	
D1	Prohibited concomitant medication	
D1.1	Prohibited medication use before the start of study treatment period	Inclusion criteria IN6 is not met. or At least one of exclusion criteria EX1-EX5 is met. or Prohibited concomitant therapy use before start of study treatment (defined in Sections 3.3.1 and 3.3.2 of the CTP).
D1.2	Prohibited medication use during study treatment period	Prohibited concomitant therapy use during study treatment (defined in Section 4.2.2 of the CTP).
D2	Mandatory medication not taken	
D2.1	Incorrect dose of radiotherapy administered during the concomitant treatment period	Radiotherapy total dose not equal to 60 Gy.
D2.2	Pneumocystis pneumonia prophylaxis not taken during concomitant treatment period (Regimen M only)	For patients in Regimen M only: Concomitant therapy use during concomitant treatment period does not include appropriate prophylaxis.
G	Trial specific protocol violations	
G1	Non-adherence to safety withdrawal criteria	Trial medication continued despite withdrawal criteria in Section 6.3 of the CTP met.
G2	Other protocol violations affecting patient rights or safety	Any other protocol violation that affects the rights or safety of trial patients.

